^o Urinalysis will include protein, glucose, ketones, urobilinogen, occult blood, and microscopic sediment evaluation. A 24-hour urine collection for assessment of urine protein will be performed whenever the urinalysis reveals \geq 3+ protein.

^p Negative serum β -hCG pregnancy test within 7 days prior to the first dose of study drug will be required as an entry criterion for WOCBP. For WOCBP, a urine sample or serum pregnancy test will be performed on Day 1 of Cycle 2-Cycle 5, then at each subsequent in-person visit while patient is on treatment (including the EOT visit).

^q See Section 5.6 and Table 10 for full PK profile and sparse PK sampling schemes. On PK collection days, patients should be instructed to wait until they arrive at the study center and receive instructions from study staff prior to taking their dose of study medication. Sparse PK will also be collected (sampling scheme: C2D1, C3D1, C4D1, C5D1 and every other cycle thereafter [\pm 2 days], 1 pre-dose sample and 2 post-dose blood draws: the 1st draw at 0.5-1.5 hours post-dose and the 2nd draw at 2-4 hours post-dose.) Refer to Table 10. Patients participating in the initial Dose Escalation where BDTX-189 was evaluated fasting should also take the study drug fasting for the detailed PK assessment. Patients receiving BDTX-189 in the non-fasting state should be provided a meal of their choice in connection with the detailed PK assessment as instructed in Section 6.1.2.

^r ctDNA samples will be obtained pre-dose on C1D1, C2D1, C3D1, and at the EOT visit and/or time of disease progression for all patients enrolling onto Part A, including Food-Effect patients. If not collected at the EOT visit, these samples may be collected at the 30-day Safety Follow-up visit as long as no new anticancer therapy has commenced. (See Section 5.7.3)

^s After dose level 5 (400 mg QD) has been deemed tolerable by the SRC, or a later cohort has been deemed tolerable based on emerging data, Food Effect will be assessed during a lead-in phase for patients in that cohort. On Day -4, patients will be randomized to receive BDTX-189 as a single oral dose after fasting for at least 10 hours before dosing or immediately after consuming breakfast. Patients receiving the study drug in the fasted state will continue to fast for at least 4 hours after the dose. Patients will receive BDTX-189 in the opposite prandial state on Day-1 (see Section [5.3.1](#)).

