^t Pharmacokinetic blood samples for the Food-Effect cohort will be taken at the time points listed in [Table 11](#). Full PK profiles will be collected on Day-4, Day 1, and C1D15. Sparse PK will also be collected (sampling scheme: C2D1, C3D1, C4D1, C5D1 and every other cycle thereafter [± 2 days], 1 pre-dose sample and 2 post-dose blood draws: the 1st draw at 0.5-1.5 hours post-dose and the 2nd draw at 2-4 hours post-dose.) Refer to [Table 10](#). On the days of PK collection, patients should be instructed to wait until they arrive at the study center and receive instructions from the research staff prior to taking their dose of study medication. Patients participating in the initial Dose Escalation where BDTX-189 was evaluated fasting should also take the study drug fasting for the detailed PK assessment. Patients receiving BDTX-189 in the non-fasting state should be provided a meal of their choice in connection with the detailed PK assessment as instructed in Section [6.1.2](#).

^u Archival tissue sample is only required for patients in Part A who have allosteric *ErbB* mutations and archival tissue available; tissue block is preferred. For patients in the Safety Expansion portion of Part A, please see [Table 2](#).

^v Patients in the Dose Escalation and Food-Effect portions of Part A will be required to undergo a fresh baseline and on-treatment tumor biopsy if the tumor is amenable for biopsy in the opinion of the Investigator. The on-treatment biopsy will be obtained from dose level 5 (400 mg) and continue at higher dose levels until data supports target engagement in downstream signaling. Fresh tumor biopsies will be collected at baseline (or within 28 days prior to C1D1), on C2D1 (± 5 days), and at the time of disease progression (the on-treatment tumor biopsy collected at disease progression will be optional for all patients who consent). On C2D1 (± 5 days), patients must be dosed in the clinic at least 2 hours prior to collecting the biopsy. The biopsy may be collected up to 8 hours after dosing. Depending on emerging data, C2D1 biopsies may be collected pre-dose (see Section [5.7.2](#)).

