1.1.8. Study Rationale and Rationale for Starting Dose

Allosteric mutations in [REDACTED] and [REDACTED] have been identified and characterized; these mutations encode molecular changes in these oncogenic targets that are not located at traditional substrate or inhibitor binding sites, but rather act at a distance to influence the binding properties of these sites. BDTX-189 is highly potent against these allosteric mutations which are found in 1% to 2% of a large variety of solid tumors but are enriched in tumors such as advanced NSCLC, invasive breast cancer, bladder cancer, and endometrial cancer. Currently available [REDACTED] and [REDACTED] TKIs or mAbs have limited or no antitumor activity against these genetic alterations either because of insufficient potency or lack of selectivity which results in toxicity before adequate exposures are achieved. Therefore, there is a high unmet medical need for a large group of patients currently not served. The goal of the development plan for BDTX-189 is to efficiently evaluate the antitumor activity across a broad range of solid tumor types expressing allosteric *ErbB* mutations.

BDTX-189 binds covalently to the ATP-binding site of the mutant receptor at very low concentrations ($IC_{50} < 77$ nM cellular potency). It has been demonstrated that BDTX-189 remains bound to mutant receptors for at least 24 hours, with site occupancy >50% at 24 hours after probe addition. This observation has been confirmed *in vivo*, where oral administration of BDTX-189 to athymic nude mice bearing allosteric *ErbB* mutant BaF3 allografts showed suppression of target phosphorylation for at least 24 hours. This indicates that BDTX-189 binds

[figure not shown]
to the active site of *ErbB* allosteric mutants via a slow off-rate or covalent mechanism supporting once daily dosing in humans.

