Patients will receive BDTX-189 as a single oral dose on Day -4 after fasting for at least 10 hours before dosing or immediately after consuming a high-fat breakfast. Patients will receive BDTX-189 in the opposite prandial state on Day -1. BDTX-189 will be administered QD in 21-day cycles starting on C1D1. On the assigned day of PK assessment in the fed state, 30 minutes prior to the planned BDTX-189 administration time, patients will be instructed to consume a high-fat meal (see below for an example breakfast) and must finish the meal within 30 minutes. Patients will be instructed to take their dose of BDTX-189 with approximately 240 mL water within 30 minutes after starting the high-fat meal. On the assigned day of PK assessment in the fasted state, BDTX-189 will be administered together with approximately 240 mL water, following an overnight fast of at least 10 hours. Patients should not consume any food for at least 4 hours after the dose. The use of agents that suppress gastric acidity (H2 receptor antagonists, proton pump inhibitors, and intraluminal antacids) and agents that delay gastric emptying are prohibited from 1 week prior to the Day -4 dose until C1D1, when only proton pump inhibitors will be prohibited, as described in Section 4.5.2. Please see Table 11 (PK Sample Collection Food Effect Part A) for specific time points.

Patients will be given a high-fat breakfast in order to assess food effects on the PK of BDTX-189. An example high-fat breakfast that will be provided is a standard McDonald's

breakfast, which might include an Egg McMuffin, bacon, hash browns, and milk. Note: Alternative food components/quantity and/or time (i.e., lunch) may be allowed as per timing of dose administration and as approved by the Investigator/Sponsor. In addition, a low-fat breakfast may also be assessed as emerging data dictate. An example low-fat breakfast may include 8 ounces of milk (1% fat), one boiled egg, and one packet flavored instant oatmeal with water (approximately 400-500 calories).

5.3.2. *Electrocardiogram Measurements*

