Single ECGs will be required pre-dose at the time points indicated in the Schedule of Assessments ([Table 1](#), [Table 2](#), and [Table 3](#)). Electrocardiograms (single) will be obtained after the patient has been resting quietly in semi-supine position for at least 5 minutes before the ECG. Electrocardiogram parameters (PR interval, QRS interval, QTcF, and heart rate) will be recorded. When multiple assessments coincide, ECGs will be done immediately before the scheduled PK sample or any other blood draw.

Time-matched triplicate ECG measurements will also be collected for patients in Part A's Dose Escalation and Food-Effect cohorts, and patients who are undergoing detailed PK assessment of a smaller and reformulated tablet in the Safety Expansion. ECG measurements will coincide with the detailed PK assessments around the projected C_{max} in patients to evaluate any corrected QT (QTc) concentration-effect relationship. These ECG measurements will be performed in triplicate pre-dose and at 1.0, 2.0, 3.0, and 4.0 hours post-dose on C1D1 and C1D15 starting with dose level 4 (200 mg) and onwards for the QD schedule and starting with dose level 1 for the BID dosing schedule, if a more frequent dosing schedule is pursued. For each set of triplicate ECGs, three standard resting 12-lead ECGs will be obtained in close succession and not more than 2 minutes apart (4 minutes total for 3 ECGs). Electrocardiograms will be obtained after the patient has been resting quietly in semi-supine position for at least 5 minutes, prior to the first ECG procedure and during the triplicate ECG collection.

Please refer to the Schedule of Assessments ([Table 1](#) and [Table 2](#)).

5.3.3. *Response Assessments*

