5.6.1. Pharmacokinetic Assessments – Food Effect (Part A)

Plasma PK parameters (including AUC_{0-INF} , $AUC_{(0-\tau)}$, C_{max} , T_{max} , $t_{1/2}$, Cl/F , and Vd/F) of BDTX-189 following oral administration in a fed/fasted state will be assessed by analysis of blood samples at the time points specified in [Table 11](#).

Table 11

BDTX-189 pharmacokinetic collection times – Lead-in phase for Food-Effect (Part A)

Study Day	PK draws (hours post-dose)	Collection window (\pm mins)
Day -4	pre-dose	
	0.5	5
	0.75	5
	1	10
	1.5	10
	2	15
	3	15
	4	20
	6	30
	8	30
Day -1	pre-dose	
	0.5	5
	0.75	5
	1	10
	1.5	10
	2	15
	3	15
	4	20
	6	30
	8	30

Abbreviations: mins = minutes; PK = pharmacokinetic.

Note: Beginning with Cycle 1 Day 15, PK sampling will continue as per all other patient cohorts (see Table 10). There is no PK sampling on C1D1 for patients in the Food-Effect cohort.

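### Food-Effect patients have no ctDNA sample from before their first (Day -4) dose, and their Cycle 1 Day 1 triplicate ECGs have no matching PK sample

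*Combined protocol and SAP*

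**What the plan says.** **Dosing.** Section 5.3.1 sets the first lead-in dose: "Patients will receive BDTX-189 as a single oral dose on Day -4 after fasting for at least 10 hours before dosing", or alternatively after a high-fat breakfast. It then adds: "Patients will receive BDTX-189 in the opposite prandial state on Day -1". Daily dosing follows from C1D1.

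**ctDNA.** Table 1 footnote r reads "ctDNA samples will be obtained pre-dose on C1D1, C2D1, C3D1, and at the EOT visit", and this holds "for all patients enrolling onto Part A, including Food-Effect patients". Section 5.7.3 gives the same list for Part A Dose Escalation and includes the Food-Effect cohort. Only Part B has a screening ctDNA sample.

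**Biopsy.** Table 1 marks the baseline biopsy in the C1D1 column, but footnote v gives a window: "Fresh tumor biopsies will be collected at baseline (or within 28 days prior to C1D1"). Section 5.2 lists the baseline biopsy among items to be recorded before treatment starts. Footnote v makes baseline and on-treatment biopsies obligatory for Food-Effect patients with an amenable tumor. The synopsis (Correlative Testing) says paired biopsies are not mandatory in that cohort.

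**ECG and PK.** Section 5.3.2 requires time-matched triplicate ECGs on C1D1 and C1D15 in the "Dose Escalation and Food-Effect cohorts, and patients who are undergoing detailed PK assessment" of the reformulated tablet. The note to Table 11 says: "There is no PK sampling on C1D1 for patients in the Food-Effect cohort". Section 5.3.1 agrees. Table 11 places full PK profiles on Day -4 and Day -1, and the ECG row of Table 1 has no entry on either day.

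**The concern.** The sampling schedule treats C1D1 as the first dose, and Section 9.5.5 describes it in those terms. For Food-Effect patients it is the third. Their first ctDNA sample is therefore taken after exposure to a drug that Section 1.1.4 calls irreversible and that, in Section 1.1.8, "remains bound to mutant receptors for at least 24 hours, with site occupancy >50% at 24 hours". Section 9.5.7 relates changes in ctDNA mutations to response, and measures the change in tissue signaling from baseline to C2D1. A baseline taken on drug would tend to understate any change that the lead-in doses had already begun.

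Section 9.4 keeps Food-Effect patients out of the DLT-evaluable population, and Section 9.5.6 analyses their PK separately. The pharmacodynamic population has no such provision, so post-dose and drug-free baselines would be pooled.

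For the ECGs, the stated purpose is a QTc concentration-effect analysis. A tracing without a concentration cannot contribute to it.

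**Working it through.** The plan states no figure on this point, so the check compares dosing days with sampling days.

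**1. Order of events for a Food-Effect patient**

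| Day | Dose | ctDNA | Full PK | Triplicate ECG |
|---|---|---|---|---|
| Screening | none | none | none | none |
| Day -4 | lead-in 1 | none | yes | none |
| Day -1 | lead-in 2 | none | yes | none |
| C1D1 | first daily dose | first sample, pre-dose | none | yes |
| C1D15 | daily dosing | none | yes | yes |

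No ctDNA sample precedes the Day -4 dose. ECGs and full PK coincide on C1D15 but not on C1D1. Footnote t of Table 1 lists a full profile on Day 1 where Table 11 has Day -1. Section 5.3.1 and Table 11 both rule out PK on C1D1, so footnote t should be reconciled with them.

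**2. Residual plasma drug at the C1D1 pre-dose sample**

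Inputs: median half-life 2.2 to 5.9 h (Section 1.1.7), and lead-in doses 72 h apart. The gap g from the Day -1 dose to C1D1 is about 24 h if there is no Day 0 and about 48 h if there is one; the documents do not say which.

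Assuming simple exponential decline, the residual as a fraction of one dose is 0.5^(g/t½) + 0.5^((g+72)/t½).

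- g = 24 h, t½ = 2.2 h: 0.05%
- g = 24 h, t½ = 5.9 h: 5.96%
- g = 48 h, t½ = 2.2 h: below 0.001%
- g = 48 h, t½ = 5.9 h: 0.36%

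Plasma carry-over is small. With irreversible binding, plasma level is not the relevant measure. Section 1.1.8 reports more than 50% site occupancy at 24 h, and target phosphorylation suppressed for at least 24 h in mice. An effect at the target on C1D1 is therefore plausible. Nothing in the documents converts it into a change in ctDNA.

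**3. Biopsy window**

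A biopsy taken between 28 days before C1D1 and the Day -4 dose is drug-free. One taken after the Day -4 dose and before C1D1 dosing is not, yet it falls inside the footnote v window.

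**4. Scope**

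- Patients: up to 16 of about 128 in Part A, 16/128 = 12.5%.
- ECGs: 5 time points (pre-dose, 1, 2, 3 and 4 h) × 3 = 15 tracings per patient on C1D1, and 15 × 16 = 240 at most. Table 11 has PK draws at the same five nominal times on both lead-in days.
- Already evaluable for food effect at 02 April 2021: 6 in each of two meal cohorts (Section 1.1.7), 6 + 6 = 12.

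**The case against.** Much of the case on the other side stands.

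- A reader might infer from the Table 1 grid that the baseline biopsy is set at C1D1. It is not: footnote v gives a 28-day window, and Section 5.2 places the biopsy before treatment starts, which for this cohort naturally means before Day -4. Only the missing express limit remains. Whether the cohort needs paired biopsies at all is unsettled.
- A reader might infer a calculable bias. If pERK were still 50% suppressed at baseline, a true 80% suppression would appear as 1 − 0.20/0.50 = 60%; at 20% residual suppression it would appear as 1 − 0.20/0.80 = 75%. Both residual values are assumptions. The occupancy figure is an assay result and the phosphorylation result comes from mice. The arithmetic also applies only to a biopsy taken after lead-in dosing, and says nothing about ctDNA.
- A reader might infer that dose or schedule selection is at risk. Both pharmacodynamic objectives are exploratory (Section 2.3), 800 mg QD non-fasting is already named as the recommended dose (Section 1.1.7), and the synopsis says BID was opened on PK and safety/tolerability. Escalation patients outside this cohort have no lead-in doses.
- A reader might infer that these patients are lost to the QTc analysis. C1D15 stays matched, and the relationship is not a listed endpoint.

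What the objection does not remove is the absence of any pre-dose ctDNA sample and the conflict between Sections 5.3.2 and 5.6.1 over C1D1.

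**Conclusion.** The point holds as a scheduling defect. Followed exactly, the plan gives up to 16 Food-Effect patients a post-dose ctDNA baseline, and 5 triplicate ECG sets each on C1D1 with no matching concentration. The biopsy window leaves room for a post-dose baseline but does not require one.

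The ctDNA consequence is a plausible risk of unknown size, confined to exploratory objectives. It rests on the protocol's nonclinical binding data being relevant to patients, and the documents do not show that two single doses alter ctDNA. The documents therefore do not support saying that the baseline is contaminated, only that it may be. The ECG mismatch needs no such assumption, since it follows from the schedule itself.

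**What to change.** For Food-Effect patients:

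1. Draw the baseline ctDNA sample pre-dose on Day -4 instead of C1D1 (Table 1 footnote r, Section 5.7.3).
2. Tie the baseline biopsy window to the first lead-in dose (footnote v, Sections 5.2 and 5.7.2). Reconcile footnote v with the synopsis on whether this cohort needs paired biopsies.
3. Place the C1D1 triplicate ECGs on a full-PK lead-in day (Section 5.3.2, Table 1). Day -4 has the advantage of a drug-free pre-dose reading. Correct footnote t at the same time.
4. For patients already enrolled, state in Section 9.5.7 or the SAP that any baseline taken after lead-in dosing is left out of change-from-baseline summaries or shown separately.

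**Cost.** The numbers of samples, biopsies and tracings do not change, and patients already attend on the lead-in days. Item 4 removes most of the planned cohort from the pooled ctDNA change summary, since 12 of up to 16 were already evaluable. Items 1 to 3 reach only the remaining patients, about 16 − 12 = 4, plus any added under the option in Section 5.3.1 to enlarge the cohort. The moved ECGs are taken at the lead-in dose (400 mg), which may differ from the C1D1 dose (400 or 800 mg under Section 5.3.1).

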^w Tumor assessment (CT or MRI of chest, abdomen, and pelvis, plus other sites of known disease at baseline) will be performed every 6 weeks (± 3 days) for the first 8 cycles, then every 12 weeks (± 7 days) thereafter, at EOT, and at the discretion of the Investigator. Imaging should be completed within a window of -3 days prior to D1 of odd cycles and should be reviewed before study drug administration on D1 for dosing determination. Tumor assessment/imaging must be performed at the time of treatment discontinuation, unless it has been done within the past 4 weeks. If disease progression according to RECIST (version 1.1) is documented at any time, no further tumor/response assessment will be required.

^x May be performed any time within 28 days prior to C1D1 and includes assessments completed at the clinical site as part of standard of care, and prior to the signing of the informed consent, if the assessments were performed in compliance with the protocol requirements. Baseline assessment must include CT or MRI imaging of the chest and abdomen, through the level of the adrenals, and brain, if clinically indicated, as well as other sites of known disease.

Table 2 BDTX-189-01 Schedule of Assessments Part A-Safety Expansion

Flow Chart (Part A Safety Expansion) Study period	Screening	Part A Safety Expansion BDTX-189 Treatment Period									
Study Procedures ^a		Cycle 1 (±1 day for Days 8, 15)			Cycle 2 (±2 days)		Cycle 3, 4, 5 and every other cycle thereafter (±2 days)	End of Treatment ^c	30-Day Safety Follow-up Visit ^d	Un-scheduled Visits ^e	PFS/OS ^x
Study Day	≤28 days prior to C1D1	1 ^b	8	15	1	8	15	1	Within 3 days of decision to discontinue study drug	30 days after last dose (±3)	
Informed consent	X ^f										
Inclusion / exclusion criteria	X										
Medical and disease history	X										
Demographics	X										
Complete physical exam ^g	X	X			X			X	X		
Directed physical exam ^g			X	X		X	X		X	X	
Weight	X	X ^h						X	X	X	
ECOG Performance Status	X	X ^h			X			X	X	X	
Vital signs ⁱ	X	X	X	X	X	X	X	X	X		
12-lead ECG ^{j,k}	X	X ^k		X ^k	X			X	X	X	
ECHO/MUGA ^l	X							X ^l	X	X	

Flow Chart (Part A Safety Expansion) Study period	Screening	Part A Safety Expansion BDTX-189 Treatment Period							End of Treatment ^c	30-Day Safety Follow-up Visit ^d	Un-scheduled Visits ^e	PFS/OS ^x
		Cycle 1 (±1 day for Days 8, 15)			Cycle 2 (±2 days)			Cycle 3, 4, 5 and every other cycle thereafter (±2 days)				
Study Procedures ^a												

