- ^s Tumor assessment (CT or MRI of chest, abdomen, and pelvis, plus other sites of known disease at baseline) will be performed every 6 weeks for the first 8 cycles, and then every 12 weeks thereafter. Imaging should be completed within a window of -3 days prior to D1 of odd cycles and should be reviewed before study drug administration on D1 for dosing determination. Patients who discontinue treatment for reasons other than PD will undergo tumor assessment in accordance with the original schedule relative to C1D1. Tumor assessment/imaging must be performed at the time of treatment discontinuation, unless it has been done within the past 4 weeks. If disease progression according to RECIST (version 1.1) is documented at any time, no further tumor/response assessment will be required.
- ^t May be performed any time within 28 days prior to C1D1 and includes assessments completed at the clinical site as part of standard of care, and prior to the signing of the informed consent, if the assessments were performed in compliance with the protocol requirements. Baseline assessment must include CT or MRI imaging of the chest and abdomen, through the level of the adrenals, and brain, if clinically indicated, as well as other sites of known disease.
- ^u From the 30-Day Safety Follow-up visit, follow-up for OS, PFS, and first subsequent anti-cancer therapy, if available, will be obtained every 3 months (\pm 14 days) until 2 years after the first dose of study drug, death, loss to follow-up, withdrawal of consent, or end of the whole trial. Follow-up information about overall survival may be obtained by phone.
- ^v Archival tissue sample is mandatory for patients in Part B who have archival tissue available; a tissue block is preferred. In the event that a tissue block is unavailable, 12-20 formalin-fixed paraffin-embedded unstained slides may be submitted. If there is not enough archival tumor tissue, a new tumor tissue biopsy sample must be obtained during screening, prior to starting study treatment. (See Section [5.7.1](#)).

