Patients will be evaluated for response to treatment after 2 cycles of treatment. Response will be assessed at 6-week intervals (± 3 days) during the first 24 weeks (8 cycles) of study treatment. Thereafter, patients will be evaluated for response to treatment every 12 weeks (± 7 days), at the EOT visit (if not performed within the previous 4 weeks), and at the discretion of the Investigator. Patients with PD or unacceptable toxicity should be discontinued from the study; patients with SD or response to therapy will continue treatment. However, patients who are receiving clinical benefit in the opinion of the treating Investigator may be allowed to stay on study beyond initial radiological progression after consultation with the Medical Monitor if it is felt that it is in the patient's best interest. The assessments to be performed at this time are specified in [Appendix B](#). All target and non-target lesions documented at screening must be assessed. Please refer to Section [7](#) for further instructions on evaluating response (e.g., PD, SD).

The following assessments will be performed if abnormal at baseline or if clinically indicated:

- CT scan or MRI of chest, abdomen, and pelvis plus any other sites of known disease.
- CT scan head/MRI brain if history of CNS metastasis.

Investigators must ensure that images of all chest and abdomen CT/MRI scans for patients enrolled in Part B are available for transmission to the Sponsor for a future central reading by a BICR committee depending on preliminary efficacy results from Part A (see separate imaging charter).

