7. RESPONSE EVALUATIONS AND MEASUREMENTS

Response and progression will be evaluated in this study using RECIST Version 1.1 (see [Appendix B](#)). Lesions are either measurable or non-measurable according to the criteria. The term “evaluable” in reference to measurability will not be used, as it does not provide additional meaning or accuracy.

At screening, tumor assessments should encompass all areas of known predilection for metastases in the disease under evaluation and should additionally investigate areas that may be involved based on signs and symptoms of individual patients. These assessments should be performed no more than 28 days before the start of study treatment and, ideally, should be performed as close as possible to the start of study treatment. The methods of assessment used at screening should be used at each subsequent follow-up assessment.

Follow-up assessments should be performed every 6 weeks (± 3 days) after the start of BDTX-189 treatment for the first 8 cycles and every 12 weeks (± 7 days) thereafter. Any other sites at which new disease is suspected should also be appropriately imaged. If an unscheduled assessment is performed and the patient has not progressed, every attempt should be made to perform subsequent assessments at the scheduled visits while the patient remains on study treatment.

Categorization of objective tumor response assessment will be based on the RECIST v1.1 criteria for response: CR (complete response), PR (partial response), SD (stable disease), and PD (progressive disease).

If the Investigator is in doubt as to whether progression has occurred, particularly with response to non-target lesions (NTLs) or the appearance of a new lesion, it is advisable to continue treatment and reassess the patient’s status at the next scheduled assessment or sooner if clinically indicated.

To achieve “unequivocal progression” on the basis of non-target disease, there must be an overall level of substantial worsening in non-target disease such that, even in presence of SD or PR in target disease, the overall tumor burden has increased sufficiently to merit discontinuation of therapy. A modest increase in the size of one or more NTLs is usually not sufficient to qualify for unequivocal PD status.

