Progressive Disease (PD): At least a 20% increase in the sum of the diameters of target lesions, taking as reference the smallest (nadir) sum since the treatment started, or the appearance of one or more new lesions. Requires not only 20% increase, but absolute increase of a minimum of 5 mm over sum.

Evaluation of Non-Target Lesions

Complete Response (CR): Disappearance of all non-target lesions and normalization of tumor markers. All lymph nodes must be non-pathological in size (<10 mm short axis).

Non-CR/Non-PD: Persistence of one or more non-target lesions and/or persistence of tumor marker level above the normal limits.

Progressive Disease (PD): Appearance of one or more new lesions and/or unequivocal progression of existing non-target lesions. When the patient also has measurable disease, to achieve “unequivocal progression” on the basis of the non-target disease, there must be an overall level of substantial worsening in non-target disease such that, even in presence of SD or PR in the target disease, the overall tumor burden has increased sufficiently to merit discontinuation of therapy.

Evaluation of Best Overall Response

The best overall response is the best response recorded from the start of the treatment until disease progression/recurrence (taking as reference for PD the smallest measurements recorded since the treatment started). In general, the patient's best response assignment will depend on the achievement of both measurement and confirmation criteria.

Confirmation of response (by repeat scans after 4 weeks or as specified in the protocol) is required for trials in which response rate is the primary endpoint but is not required in randomized trials or trials with primary survival endpoints (i.e., where response is not a primary endpoint).

Note that a best overall response of SD requires an assessment of SD or better at the time of the first protocol-specified post-baseline tumor assessment (i.e., 42 days +/- 3 days after first dose) or later.

Target Lesions	Non-Target Lesions	New Lesions	Overall Response
CR	CR	NO	CR
CR	NON-CR/NON-PD	NO	PR
CR	NE	NO	PR
PR	NON-CR/NON-PD OR NE	NO	PR
SD	NON-CR/NON-PD OR NE	NO	SD
NOT ALL EVALUATED	NON-PD	NO	NE
PD	ANY	YES OR NO	PD
ANY	PD	YES OR NO	PD
ANY	ANY	YES	PD

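### Baseline and follow-up imaging fields conflict: no passage expressly requires the pelvis at screening, so a pre-existing lesion can be scored as new

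*Combined protocol and SAP*

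**What the plan says.** Four sets of text bear on the imaging field.

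- **Screening footnotes** (Table 1 x, Table 2 v, Table 3 t, same wording). "Baseline assessment must include CT or MRI imaging of the chest and abdomen, through the level of the adrenals, and brain, if clinically indicated", and the sentence goes on "as well as other sites of known disease". The footnotes also accept standard-of-care scans taken before consent if they comply with the protocol.
- **Tumor-assessment row footnotes** (Table 1 w, Table 2 t, Table 3 s). In Table 3: "Tumor assessment (CT or MRI of chest, abdomen, and pelvis, plus other sites of known disease at baseline) will be performed every 6 weeks". These footnotes sit on the row label, and the row includes the Screening cell.
- **Section 7.** "At screening, tumor assessments should encompass all areas of known predilection for metastases in the disease under evaluation", together with areas suggested by signs and symptoms. It adds: "The methods of assessment used at screening should be used at each subsequent follow-up assessment".
- **Section 5.3.3.** "The following assessments will be performed if abnormal at baseline or if clinically indicated", followed by a bullet for chest, abdomen and pelvis plus known sites. For central reading it names only chest and abdomen images for transmission, whereas Section 10.3.3 has the BICR review all available scans.

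For non-target disease, Appendix B defines PD as "Appearance of one or more new lesions and/or unequivocal progression of existing non-target lesions", and its overall-response table makes any new lesion PD. It has no rule for a lesion in a region that was not imaged at baseline. Under Section 9.2, a patient with PD before CR or PR is a non-responder.

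**The concern.** A new lesion can be called new only if the same region was imaged before. If a site scans to the adrenals at screening and through the pelvis at Week 6, a small pelvic or lower abdominal lesion that was already there, but unknown, first appears at Week 6. Appendix B then scores PD.

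PD before response fixes the patient as a non-responder for the Part B primary endpoint and adds an early PFS event. The primary endpoint also needs confirmation at least 4 weeks later, and Table 3 footnote s requires no further tumor assessment once PD is documented. So an investigator's PD call can remove the confirming scan even if central review never sees the pelvic lesion. The futility rules use assessments up to 6 weeks, which is the first scan at which the two fields could differ.

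A site that follows 5.3.3 errs the other way. It may not rescan regions that were normal at baseline, so true new lesions are found late or missed, and PFS and DOR lengthen. ORR, PFS and DOR would then depend partly on which passage a site follows.

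**Working it through.** **Step 1: the passages side by side.**

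| Text | When it applies | Field | Force |
|---|---|---|---|
| Footnotes x / v / t | Screening cell | Chest; abdomen to adrenals; brain if indicated; known sites | Mandatory minimum |
| Footnotes w / t / s | Row label; six-weekly scans, possibly Screening | Chest, abdomen, pelvis; known sites | Stated as performed |
| Section 7 | Screening | Predilection areas; areas with signs or symptoms | Advisory, no named field |
| Section 5.3.3 | On treatment | Chest, abdomen, pelvis; known sites | Conditional |

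A site can meet the explicit screening minimum without a pelvic scan. The exposed lesions are those unknown at baseline, outside the minimum field, and not picked up through Section 7.

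**Step 2: reproduce the plan's figures.** The inputs are the stopping and success rules in Section 9.3.2. With response probability p:

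- Cohorts 1 and 2: power = P(X₁₅ ≥ 1, X₃₁ ≥ 7, X₈₅ ≥ 21)
- Each Cohort 3 or 4 subgroup: power = P(X₁₀ ≥ 1, X₂₉ ≥ 4)
- Cohort 5: power = P(X₃₀ ≥ 4, X₈₉ ≥ 14)

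First-stage stopping can be checked by hand: 0.825¹⁵ = 0.0558 and 0.70¹⁵ = 0.0047 (Table 12); 0.95¹⁰ = 0.5987 and 0.80¹⁰ = 0.1074 (Tables 13 and 14). Exact binomial enumeration over all stages gives type I error / power of 0.0459 / 0.8008, 0.0468 / 0.8011 and 0.0478 / 0.8018. Tables 12 to 15 are reproduced to four decimals.

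**Step 3: illustrate a loss of responders.** Let f be the share of would-be responders scored PD for an old lesion outside the baseline field. The response probability becomes p(1 − f), for example 0.30 × 0.95 = 0.285. **f is an assumption; the documents give no value.** As in the plan's tables, one response probability is used at every stage.

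| f | Cohorts 1, 2: ORR, power | Cohort 3/4 subgroup: ORR, power | Cohort 5: ORR, power |
|---|---|---|---|
| 0 | 0.300, 0.801 | 0.200, 0.801 | 0.200, 0.802 |
| 2% | 0.294, 0.772 | 0.196, 0.788 | 0.196, 0.779 |
| 5% | 0.285, 0.723 | 0.190, 0.768 | 0.190, 0.742 |
| 10% | 0.270, 0.628 | 0.180, 0.730 | 0.180, 0.671 |

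In patients, a full Cohort 1 at the target rate expects 85 × 0.30 = 25.5 responders. An f of 5% is 25.5 × 0.05 ≈ 1.3 of them.

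**Step 4: direction of the error.** If responders under the null are lost at the same 5% rate, type I error also falls: 0.0459 to 0.0284 in Cohorts 1 and 2, 0.0468 to 0.0400 in a Cohort 3 or 4 subgroup, and 0.0478 to 0.0334 in Cohort 5. For ORR the error costs power and does not produce false claims of activity. The opposite effect on PFS and DOR under 5.3.3 cannot be quantified from the documents.

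**The case against.** The strongest reply is that the footnotes can be read together. The chest, abdomen and pelvis footnote labels the whole row, Screening included, and the screening footnote then only sets a floor. Section 7 widens screening further, and known sites must be imaged in any case. On that reading the pelvis is covered, at least where it is a predilection site. This is a fair reading, and it defeats the inference that the plan restricts baseline imaging to the adrenals. It does not remove the ambiguity: the screening footnote is the only text that names a mandatory baseline field, and Section 7 is advisory and names none.

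Three other stronger inferences also fail:

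- **That a false PD necessarily ends treatment and scanning.** Section 7 advises continuing and reassessing when a new lesion is in doubt. Sections 3.3 and 5.3.3 let patients with clinical benefit stay on study after consultation. Further scans are not required after PD, but they are not forbidden.
- **That 5.3.3 sets a third imaging field.** It names the same field as the row footnotes and adds a condition. Where a region is not rescanned, it cannot produce a false new lesion, so the two harms pull in opposite directions.
- **That the BICR endpoint is certainly affected.** For a pelvic lesion, the direct route depends on whether pelvic images are sent, and 5.3.3 and 10.3.3 differ on this. Adjudication is left to the imaging charter, which is not among the documents and may deal with regions lacking a baseline image.

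**Conclusion.** The point stands as a conflict between passages that should be fixed. It appears in all three schedules, and a site that complies with the explicit screening minimum can create a false PD. The effect on ORR is conservative. The effect on PFS and DOR depends on the passage followed.

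The size is unknown. The figures of 77%, 72% and 63% for Cohorts 1 and 2 rest entirely on assumed losses of 2%, 5% and 10% of responders, and should not be read as an estimate of lost power. To be lost, a would-be responder needs a lesion that is unknown and unscanned at baseline, visible at follow-up, and scored as new while target disease responds. The documents do not say how often that happens, and nothing in them supports treating this as a threat to the validity of a positive ORR result.

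**What to change.** 1. In Table 1 footnote x, Table 2 footnote v and Table 3 footnote t, name chest, abdomen and pelvis as the baseline field. Keep brain if clinically indicated and other known sites.
2. In Section 5.3.3, remove the condition from the chest, abdomen and pelvis bullet so that it matches the row footnotes.
3. Align the image-transmission sentence in 5.3.3 with Section 10.3.3, so that pelvic images reach the BICR.
4. State in Appendix B, and in the imaging charter if it does not already do so, how a lesion first seen in a region without a baseline image is scored.

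No sample size or decision boundary changes. The pelvis is added to the same CT session. The cost is that some standard-of-care scans that omit the pelvis would no longer serve as baseline and would have to be repeated or extended. The change is best made before Part B enrolls, because a missing pre-dose scan cannot be recovered later.
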